Profiling the Skin Microbiome in Response to Altreno in Acne Patients

NCT #: 04548349

Document Date: June 15, 2020

Study Design

This is a single-center, prospective study.

Study Population

Up to 60 subjects who meet study inclusion/exclusion criteria will be recruited into the study.

Materials and Methods

We will prospectively recruit healthy controls and acne patients from the BIDMC dermatology clinic as follows:

- **Control Group:** We will recruit up to 20 healthy controls without any skin diseases.
- **Experimental Group:** We will recruit up to 40 patients with acne with severity that warrants initiation of a topical medication and randomize 20 patients into Altreno 0.05% lotion monotherapy (applied once daily) and 20 patients into BPO 2.5% leave-on gel monotherapy (applied once or twice daily as tolerated).

Control Group will undergo skin swab at baseline and approximately 120 days later without any intervention. During the entire study period, the Group will not be allowed to use any antibacterial wash, other than approved OTC cleansers. *If due to the pandemic, subjects cannot return for 2nd visit in 120 days, the subjects will still remain in the study until able to do so.

Experimental Group will undergo skin swab at baseline, as well as clinical scoring of acne. Then, they will be prospectively divided 1 to 1 into Altreno group or BPO group. During the following 90 days, the Group will only be allowed to use either Altreno or BPO. On the second visit (90 days +/- 5 days), their acne will be scored again, and repeat skin swab will be taken. If significant improvement, they will be asked to discontinue the therapy for 30 days. If no significant improvement, they will be instructed to continue the therapy for additional 30 days. On the third visit (120 days +/- 5 days from the first visit), their acne will be scored, and repeat skin swab will be taken. *If due to the pandemic, subjects cannot return for subsequent visits, the subjects will either continue the therapy (or continue without therapy) and remain in the study until able to return for the subsequent visits.

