All skin swab samples will be stored at -80 °C until further processing. CoreBiome will receive skin swabs (with subject ID only, no other PHI), they will extract DNA, and perform 16S rRNA gene and/or shotgun metagenomic sequencing. Corebiome will send the BIDMC research team the raw data. The research team will be doing the bioinformatics/analysis, not CoreBiome. If, after sending the skin swabs, subject withdraws, then the PI will ask Corebiome to destroy the sample and they will not perform DNA extraction or 16S rRNA/shotgun metagenomic sequencing.

Control Group:

Procedures and Measurements	Visit 1	Visit 2
Procedures and Measurements	Screening Day 0	Day 120 +/- 5 days
Informed Consent, HIPPA Auth, Photo Release	X	
Review Inclusion/Exclusion Criteria	X	
Review of Demographics	X	
Review of Medical/Surgical Histories	X	X
Review of Current Medications	X	X
Physical Examination of Unaffected Skin	X	X
Regular Photography	X	X
Skin Swabs	X	X
Assess for Adverse Events	X	X

Experimental Group:

Procedures and Measurements	Visit 1	Visit 2	Visit 3
Procedures and Measurements	Screening Day 0	Day 90 +/- 5 days	Day 120 +/- 5 days
Informed Consent, HIPPA Auth, Photo Release	X		
Review of Inclusion/Exclusion Criteria	X		
Review of Demographics	X		
Review of Medical/Surgical Histories	X	X	X
Review of Current Medications	X	X	X
Review of Acne Histories	X		
Review of Past/Current Acne Medications	X		
Physical Examination of Acne Skin	X	X	X
Acne Leeds Score	X	X	X
Acne PGA Score	X	X	X
Regular Photography	X	X	X
Skin Swabs	X	X	X
Assess for Adverse Events	X	X	X

Data Analysis

Primary Study Parameter(s): The primary outcome of this study is assessing for changes in skin microbial composition in acne patients after treatment with Altreno or BPO by specifically comparing their skin microbiomes (1) at baseline, (2) after 3 months of treatment, and (3) 1 month 10 after discontinuation of treatment. Comparisons of species diversity and relative abundance of the identified species will be made across healthy controls, Altreno group, and BPO group.

The raw sequencing data will be first processed into taxonomic features using the standardized DADA2 protocol as implemented in the bioBakery. Then, we will analyze the

three available microbial features (taxa, alpha diversity summary statistics, and community structure via beta diversity) across the three groups defined above.

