Secondary Study Parameter(s): The clinical severity will also be correlated to the presence and/or dominance of *P. acnes* and other populations using the following measures:

- **Physician Global Assessment of Acne:** Categorical variable. A chi-square test will be performed for analysis.
- **Leeds Acne Score:** Ordinal variable. A correlation analysis and depending on distribution, one-way ANOVA, a Kruskal Wallis or a Wilcoxon rank sum test will be performed for analysis.

Other Study Parameter(s): Patient characteristics and demographics data will be presented using descriptive statistics. At every visit, adverse events and changes in medications will be registered.

Statistical Analysis Plan (per Diversigen, who performed computational analysis)

“To examine differences in abundance for taxa between treatment groups and across time, we examined taxa abundances at the Phylum, Family, Genus and ASV levels using the ASV count table as inputs. At each level of interest, count abundances were aggregated then transformed using the centered log ratio (CLR) transformation as implemented in the ALDEx2 R package. Briefly, transformation was performed using the `aldex.clr()` function, which estimates sequencing technical variation using Monte-Carlo sampling ($n = 128$) and generates CLR-transformed tables for each instance. A median CLR value for each taxon across all MC instances calculated and used for downstream plotting purposes.

Next, we performed differential abundance testing using LME models of the following model:

- `taxon_abundance ~ Treatment_Cohort*Timepoint + (1|SubjectID)`

Pairwise contrast p-values for all relevant Treatment_Cohort and Timepoint comparisons were extracted from the model using `emmeans()`. Next, p-values were corrected for multiple hypothesis correction across all taxa tested using the FDR method. Finally, all adjusted p-values generated by testing were averaged across all 128 MC instances to obtain a `padj` value for each taxon for each pairwise comparison of interest.

Using our standard significance thresholds of $padj < 0.05$, we found no taxa as significantly different in abundance at any level in any of the pairwise comparisons we examined. Therefore, we relaxed our threshold to $padj < 0.2$, which is less conservative but has been reported in the literature. Under this threshold, we found a few taxa that were significantly different.”

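### The plan links Leeds score to P. acnes without saying which visits enter or how patient, visit and arm are handled; if visits are pooled, clustering and treatment trends can create a false association

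*Combined protocol and SAP*

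**What the plan says.** The Experimental Group schedule table lists "Acne Leeds Score" and skin swabs at all three visits: Day 0, Day 90 and Day 120. Materials and Methods agrees. At the second visit "their acne will be scored again, and repeat skin swab will be taken", and then "On the third visit (120 days +/- 5 days from the first visit), their acne will be scored, and repeat skin swab will be taken". On sample size it says "We will recruit up to 40 patients with acne with severity that warrants initiation of a topical medication", and on allocation "they will be prospectively divided 1 to 1 into Altreno group or BPO group".

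Under Secondary Study Parameter(s) the aim is stated as "The clinical severity will also be correlated to the presence and/or dominance of" *P. acnes* and other populations. For Leeds, which is labelled ordinal, the method is "A correlation analysis and depending on distribution, one-way ANOVA, a Kruskal Wallis or a Wilcoxon rank sum test will be performed". The section does not say which visits are used, whether they are combined, what defines the groups for the group tests, or how patient and arm enter.

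The Statistical Analysis Plan section has one longitudinal model. Its outcome is taxon abundance, with treatment cohort by timepoint and a random subject intercept. Leeds does not appear in it.

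**The concern.** The three group tests assume independent observations, and the type of correlation is not given. Each way of choosing the visits has a different consequence:

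- **All visits pooled.** Each patient is counted up to three times. Both treatments start after Day 0, so severity and *P. acnes* can both fall with time and appear linked even when they are unrelated within patients.
- **One post-baseline visit.** Clustering and the time trend disappear. If the two treatments act differently, arm can still drive both measures.
- **Baseline only.** Valid, but it answers a between-patient question and does not use the change that the later visits record.

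Day 120 adds a further difficulty, because whether a patient is on or off treatment then depends on improvement at Day 90.

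No other analysis of Leeds is planned. A positive result that does not state its visits and unit of analysis could not separate severity tracking *P. acnes* from both having changed after treatment.

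**Working it through.** The plan gives no figure for this analysis (no power, effect size, SD or alpha), so there is nothing to reproduce. The check measures the false-positive rate under each reading.

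**Inputs from the document.** 40 patients, 20 per arm, 3 visits: 40 × 3 = 120 pairs.

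**Assumed.** Two-sided 0.05; intra-patient correlation (ICC) 0 to 0.7, equal for both measures; falls of 0 to 1 SD after baseline on average, the same at Days 90 and 120; groups for the group tests formed by splitting *P. acnes* at its median (rank sum) or tertiles (Kruskal-Wallis, ANOVA).

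**Clustering alone.** With 3 visits and the same ICC in both measures, the variance of the pooled correlation is inflated by about 1 + 2·ICC². The effective number of pairs is 120/(1 + 2·ICC²), and the rejection rate is about P(|Z| > 1.96/√(1 + 2·ICC²)).

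| ICC | Inflation | Effective pairs | Cut-off | Approximate rejection |
|---|---|---|---|---|
| 0.3 | 1.18 | 101.7 | 1.80 | 7% |
| 0.5 | 1.50 | 80.0 | 1.60 | 11% |
| 0.7 | 1.98 | 60.6 | 1.39 | 16% |

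**Shared trend.** The visit pattern (0, 1, 1) has variance 2/9. Falls of dL and dP in SD units induce r = dL·dP·(2/9)/√[(1 + 2dL²/9)(1 + 2dP²/9)].

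- 0.5 SD in both: 0.0556/1.0556 = 0.053
- 0.8 SD in both: 0.1422/1.1422 = 0.125
- 1 SD in both: 0.2222/1.2222 = 0.182

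**Simulation.** 4,000 trials per row, with Leeds and *P. acnes* unrelated given patient, visit and arm. The Monte Carlo standard error at 5% is √(0.05 × 0.95/4000) = 0.34 percentage points. The last column is a partial correlation adjusted for patient and arm-by-visit, with 120 − 40 − 4 − 1 = 75 degrees of freedom.

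| ICC; fall in both measures | Pooled Spearman | Pooled group tests | Day 90 only, Spearman | Within-patient, arm-by-visit |
|---|---|---|---|---|
| 0; none | 4.6% | 4.8–5.3% | 5.2% | 5.2% |
| 0.5; none | 9.9% | 7.7–8.9% | 4.8% | 4.6% |
| 0.7; none | 16.2% | 13.8–14.5% | 5.7% | 4.9% |
| 0.5; 0.5 SD | 13.5% | 10.6–11.0% | 4.9% | 5.1% |
| 0.5; 0.8 SD | 30.9% | 20.1–23.2% | 5.5% | 4.8% |
| 0.5; 1 SD | 52.4% | 38.4–39.6% | 4.6% | 5.6% |
| 0.5; 0.4 vs 1.2 SD by arm | 58.8% | 44.2–46.7% | 12.2% | 4.5% |
| 0.5; 0 vs 1.6 SD by arm | 97.8% | 92.9–94.4% | 79.4% | 5.0% |

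The first row shows that the simulation is calibrated. Baseline-only Spearman stayed at 4.6–5.5% in every row. Across ICC 0.3 to 0.7, pooled Spearman ran at about 7–17% with no shift, 11–18% with 0.5 SD and about 52% with 1 SD.

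**Is adjusting for visit alone enough?** No. An arm main effect is constant within a patient and cannot influence a within-patient coefficient, so visit and arm as additive terms leave arm-specific trends in place. With ICC 0.5, a within-patient test adjusted for visit but not arm-by-visit rejected in 13–14% of null trials for falls of 0.4 vs 1.2 SD, and in 25% for 0 vs 1 SD. Adding arm-by-visit terms restored about 5%.

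**The case against.** A reader might infer that the plan pools the visits, or commits to invalid tests that ignore patient, visit and arm. The text does not support that. It is silent on which visits enter, and a correlation of unstated type could be a repeated-measures version or a correlation of changes. Baseline-only testing holds its level, and so does single-visit testing when the arms act alike. What remains is that the silence permits very different analyses, and some of them are badly misleading.

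A reader might also take the 52% as this trial's error rate. The ICC and the shifts are not in the documents, and the 1 SD setting needs *P. acnes* to fall by that much. The Statistical Analysis Plan section reports that no taxon differed at the standard adjusted threshold of 0.05. With 20 patients per arm, a 1 SD fall would give a paired test 95–100% power at p < 0.05 and 72–99% at p < 0.005 (ICC 0.3 to 0.7). Correction across taxa, the unnamed findings at the relaxed 0.2 threshold and possible under-recruitment mean that 1 SD is not excluded. The documents' only results give it no support, however, and the 0 to 0.5 SD rows deserve more weight.

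It is also fair to say that this is a secondary analysis with no stated alpha or confirmatory claim, and that whether more severe patients carry more *P. acnes* is a legitimate question which a baseline correlation answers. Both points stand. They argue for reporting the between-patient association as well, not for leaving the unit of analysis open.

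**Conclusion.** The concern holds as a gap in specification with a real consequence. The plan does not fix the visits or the unit of analysis for its only Leeds analysis, and the named methods carry no term for patient, visit or arm. The size is conditional on pooling and on the assumed values: about 7–17% false positives from clustering alone, 11–18% with modest shared falls and about 52% with large ones, against a nominal 5%. Trends that differ by arm can push it higher, and they also affect a single post-baseline visit. These are ranges under assumptions, not estimates from this trial's data. The matter should be settled before any Leeds association is interpreted.

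**What to change.** 1. In acne patients only, fit `Leeds ~ within-patient deviation of P. acnes CLR + patient-mean P. acnes CLR + Treatment_Cohort*Timepoint + (1|SubjectID)`. Report the within-patient and between-patient coefficients separately. With complete data the within-patient coefficient is the same contrast as in the last column of the simulation table. The arm-by-visit terms are needed; additive terms are not enough.
2. Because Leeds is called ordinal, add a rank-based sensitivity analysis: Spearman of the Day 0 to Day 90 changes in Leeds and in *P. acnes* CLR within each arm, combined across arms. This also avoids Day 120, where treatment status depends on the Day 90 result and the arm-by-visit terms do not capture it.
3. Limit the simple tests now named to baseline, and state how the groups are formed.
4. Label the analysis with the date it was specified, since the Statistical Analysis Plan section already reports completed taxon analyses.

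The Physician Global Assessment is scored at the same three visits and assigned a chi-square test, so it needs the same statement of which visits enter.

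The cost is plan wording and a few lines of code, with no new data. The association may come out weaker than a pooled correlation would show.

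### Cross-sectional contrasts with the non-randomised healthy controls come from a model with no age or sex term, so demographic imbalance is mixed with the acne or treated-state difference.

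*Combined protocol and SAP*

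**What the plan says.** - **Who is randomised.** Materials and Methods randomises acne patients only: "randomize 20 patients into Altreno 0.05% lotion monotherapy", with 20 more to BPO. The controls are a separate group: "We will recruit up to 20 healthy controls without any skin diseases". The visible text describes no matching or stratification on age or sex.
- **What is compared.** Under Data Analysis, Primary Study Parameter(s), the primary outcome is change in the acne patients' skin microbiome from baseline, through treatment, to a month after stopping. The same paragraph then adds: "Comparisons of species diversity and relative abundance of the identified species will be made across healthy controls, Altreno group, and BPO group".
- **The model.** The Statistical Analysis Plan gives one differential-abundance model, "taxon_abundance ~ Treatment_Cohort*Timepoint + (1|SubjectID". It then states: "Pairwise contrast p-values for all relevant Treatment_Cohort and Timepoint comparisons were extracted from the model". P-values are FDR-adjusted across taxa, and the adjusted values are averaged over 128 Monte-Carlo instances.
- **Demographics.** "Review of Demographics" is marked at Visit 1 in both schedule tables. The only stated use is under Other Study Parameter(s): "Patient characteristics and demographics data will be presented using descriptive statistics".
- **Outcome of the analysis.** No taxon reached padj < 0.05 in any pairwise comparison. The plan continues: "Therefore, we relaxed our threshold to $padj < 0.2$, which is less conservative but has been reported in the literature". A few taxa were then declared.

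**The concern.** People without skin disease who agree to be swabbed may differ in age or sex from patients starting a topical acne medication. If abundance of a taxon varies with age or sex, a control-v-patient contrast at one visit estimates two things together: the acne (or treated-state) difference and the demographic difference. The random subject intercept does not separate them. It accounts for correlation among one person's repeated swabs; it does not adjust a comparison between groups.

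The error can go either way. A taxon can be declared when acne has no effect on it, or a real difference can be masked. FDR adjustment is no safeguard, because it takes each p-value as valid for the question asked. This bears on interpretation here because the only declared taxa passed the relaxed 0.2 threshold. For any that come from a control contrast, demographic imbalance is a rival explanation that the reported analysis cannot exclude.

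**Working it through.** The documents give no effect size, SD, power or demographic summary, so there is no stated figure to reproduce. The check sorts the contrasts by exposure and then illustrates the size.

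**1. Which contrasts are exposed.** Suppose age or sex adds a fixed amount to a subject's value at every visit.

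| Contrast | Demographic effect |
|---|---|
| Altreno or BPO v control, baseline | Remains in full |
| Altreno or BPO v control, day 120 | Remains in full |
| Altreno v BPO, same visit | Zero in expectation (randomised); chance imbalance possible at 20 per arm |
| Change within patients | Cancels |
| Change in patients minus change in controls | Cancels |

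**2. Inputs.** From the documents: up to 20 controls, 20 Altreno and 20 BPO. Assumed: an age gap *d* of 0.5 to 1 SD between a treatment cohort and controls, a within-group correlation *r* of 0.2 to 0.4 between age and the taxon's CLR value, and outcome SD 1.

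**3. Formulas.**
- SE = √(1/20 + 1/20) = 0.316 SD.
- Bias = *d* × *r*.
- Type I error = P(|Z + bias/SE| > 1.96).

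**4. False declaration, single test at nominal 5%.**

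| *d* | *r* | Bias (SD) | Bias/SE | Type I error |
|---|---|---|---|---|
| 0.5 | 0.2 | 0.10 | 0.316 | 6.2% |
| 1.0 | 0.2 | 0.20 | 0.632 | 9.7% |
| 1.0 | 0.3 | 0.30 | 0.949 | 15.8% |
| 1.0 | 0.4 | 0.40 | 1.265 | 24.4% |

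**5. Masking.** A true difference of 0.886 SD has 80% power at 20 v 20, since 0.886/0.316 − 1.96 = 0.84. With bias in the opposite direction, power is Φ(0.84 − bias/SE). A bias of 0.10 SD gives Φ(0.53) = 70%; a bias of 0.40 SD gives Φ(−0.42) = 34%.

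**6. Simulation of the stated model.** 200 runs, 20 per cohort, controls at days 0 and 120, patients at days 0, 90 and 120, assumed intraclass correlation 0.5, no true difference. The assumption was deliberately stronger than the range above: *d* = 1, *r* = 0.5.

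| Contrast | Unadjusted: mean, rejection | With covariate: mean, rejection |
|---|---|---|
| Altreno v control, day 0 | 0.46 SD, 35.5% | 0.02 SD, 5.5% |
| Altreno v control, day 120 | 0.44 SD, 26.5% | 0.01 SD, 2% |
| Altreno v BPO, day 120 | −0.04 SD, 2% | 0.00 SD, 7.5% |
| Altreno change, day 0 to 120 | −0.01 SD, 7.5% | 0.01 SD, 6.5% |
| Difference in change v controls | −0.02 SD, 8% | −0.01 SD, 5% |

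The formula in step 3 gives bias 0.50 SD and rejection 35.3% for this case. With 200 runs the simulation error is about √(0.35 × 0.65/200) = 3.4 points near 35% and √(0.05 × 0.95/200) = 1.5 points near 5%. The rates are therefore rough, but the pattern agrees with step 1: the bias sits in the cross-sectional control contrasts, and the covariate removes it.

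**The case against.** **The primary outcome is a within-patient comparison.** This stands. A reader might infer that the primary result or the treatment comparison is confounded. The documents do not support that: the primary outcome is defined as change in acne patients, and Altreno v BPO is randomised. The control comparison shares the paragraph, but it is a further comparison.

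**The size is assumed.** This also stands. No demographics are given. Eligibility criteria are referred to but not shown, so age limits or matching there cannot be excluded. A 1 SD age gap is a strong assumption, and the mildest case is barely above 5%.

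**Pooling overstates it.** Comparing all 40 patients with 20 controls (SE √(1/40 + 1/20) = 0.274) would give about 6.5%, 19.5% and 31% for biases of 0.10, 0.30 and 0.40 SD. The plan extracts pairwise cohort contrasts and names three groups, so 20 v 20 is the better basis. That controls are a level of Treatment_Cohort is itself an inference from the three-group comparison, though the natural one.

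**A single-test 5% rate is not the decision rule.** Correct. Nothing passed padj < 0.05, so no false declaration arose at the standard threshold. The percentages show how individual p-values would be distorted before the FDR step; they do not predict how many taxa were wrongly declared at 0.2.

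**The analysis is already done.** The plan section is a past-tense report, so any adjustment now is post hoc. That limits how the result is labelled, not whether it is informative.

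None of this supplies an adjustment for the cross-sectional control contrasts.

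**Conclusion.** The point holds for cross-sectional contrasts with healthy controls at baseline and day 120, and only there. Those contrasts mix the acne or treated-state difference with any age or sex imbalance, and the stated model cannot separate them. Under the assumed gap of 0.5 to 1 SD and correlation of 0.2 to 0.4, the single-test type I error is about 6% to 24% at 20 v 20. The direction and true size are unknown.

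The protection of the change contrasts rests on demographic effects being additive and constant over time. It is also assumed that the demographics recorded include age and sex.

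A reader might go further and infer that the taxa declared at padj < 0.2 are demographic artefacts. The text does not say which comparisons they came from and gives no evidence of imbalance, so that cannot be concluded. This is a worthwhile, inexpensive improvement to the control comparisons, not a defect in the randomised comparison.

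**What to change.** 1. Report age and sex by cohort (controls, Altreno, BPO).
2. For the control contrasts, rerun the LME with age (continuous) and sex as fixed effects. Show the result beside the unadjusted one and label it post hoc. With about 20 controls, keep the adjustment to these two terms.
3. For each taxon declared at padj < 0.2 in a control contrast, state whether it persists after adjustment.
4. State in the text that cross-sectional control contrasts are observational.

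**Cost.** A rerun and some added wording, using data the schedules already collect. Swabs were to go to the laboratory under subject ID alone, so demographics may need linking to those IDs for whoever runs the model.

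There is some loss of precision if age differs between cohorts. As a rough single-visit guide with a 1 SD gap and three cohorts of 20 (57 within-cohort degrees of freedom), the variance factor goes from 1/20 + 1/20 = 0.100 to 0.100 + 1²/57 = 0.118, about 18% more. With one treatment cohort and controls only (38 degrees of freedom) it becomes 0.126, about 26% more. Variance explained by age offsets part of this. If ages overlap poorly, the adjusted estimate relies on extrapolation and should be reported with that caution.

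### FDR correction is described across taxa only, not across contrasts or the four taxonomic levels, so the few taxa reported at padj < 0.2 cannot be told from chance

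*Combined protocol and SAP*

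**What the plan says.** The section headed Statistical Analysis Plan (per Diversigen) states that "we examined taxa abundances at the Phylum, Family, Genus and ASV levels", with counts aggregated and CLR-transformed at each level. One mixed model is fitted per taxon, with cohort, timepoint, their interaction and a random subject intercept. Then "Pairwise contrast p-values for all relevant Treatment_Cohort and Timepoint comparisons were extracted from the model", and "p-values were corrected for multiple hypothesis correction across all taxa tested using the FDR method". The adjusted p-values are averaged over 128 Monte-Carlo instances, giving one padj per taxon per comparison.

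The section does not list the relevant comparisons, name the FDR variant, say whether p-values were pooled over contrasts or levels, or give the adjustment setting used in emmeans. It reports that nothing passed padj < 0.05 at any level in any comparison. The cut-off was then relaxed to 0.2, and a few taxa were described as significantly different.

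The Data Analysis section sets the primary focus on acne patients at baseline, after three months of treatment and one month after stopping. It adds: "Comparisons of species diversity and relative abundance of the identified species will be made across healthy controls, Altreno group, and BPO group".

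**The concern.** FDR control inside one family of taxa says nothing about the error rate over many such families when a hit in any of them is reported. If each contrast at each level is its own family, each has its own allowance. At the cut-off that produced the reported taxa, that allowance is 20%. The four levels also re-test aggregates of the same counts.

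At stake is whether the taxa described as significantly different carry any evidence. A reader will take padj < 0.2 to mean that about one reported taxon in five is false. With many separate families and no true differences, the whole list can be false.

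**Working it through.** The documents give no family count or overall error rate, so there is no stated figure to reproduce.

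**Step 1: contrasts implied by the schedule.** Controls are swabbed twice ("Control Group will undergo skin swab at baseline and approximately 120 days later without any intervention"). Each acne arm is swabbed at days 0, 90 and 120. That makes 2 + 3 + 3 = 8 cohort-by-visit cells.
- Within cohort: 1 + 3 + 3 = 7.
- Between cohorts at the same visit: 3 (day 0) + 1 (day 90) + 3 (day 120) = 7.
- Total: 14. Acne arms only: 3 + 3 + 3 = 9. All pairs of cells: 8 x 7 / 2 = 28.

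**Step 2: families if FDR is run per contrast and level.** 14 x 4 = 56; low 9 x 4 = 36; high 28 x 4 = 112.

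**Step 3: no true differences, before averaging.** BH at level q then rejects something in a family with probability about q. For k independent families, P(any) = 1 - (1 - q)^k, and the expected number of families with a hit is kq.

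| k | P(any), q = 0.05 | Expected families | P(any), q = 0.2 | Expected families |
|---|---|---|---|---|
| 36 | 84.2% | 1.8 | 99.97% | 7.2 |
| 56 | 94.3% | 2.8 | 99.9996% | 11.2 |
| 112 | 99.7% | 5.6 | about 100% | 22.4 |

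The families share cells and nest across levels. A null simulation with that dependence used 20 per group, 56 families, within-subject correlation 0 or 0.5, between-level correlation 0 to 1, and assumed taxa counts of 300/100/40/10 from ASV to phylum. It gave 84-93% at 0.05 and at least 99.9% at 0.2. One BH step pooled over all taxa, contrasts and levels gave 4-6% and 17-22%.

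**Step 4: effect of averaging padj.** Averaging lowers these figures by an amount that depends on Monte-Carlo noise, which the documents do not give. Two kinds of null simulation bracket it, both with 56 families and BH per family. The count-based runs used 128 instances, assumed 300/80/45/8 taxa, and 60 runs per setting. The noise-share runs fixed the Monte-Carlo share of test-statistic variance and used 32 instances and 150 runs.

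| Setting (assumed) | Any hit at 0.05 | Any hit at 0.2 | Mean hits at 0.2 |
|---|---|---|---|
| 20,000 reads, even | 70% | 100% | 11.6 |
| 20,000 reads, more uneven | 70% | 98% | 9.4 |
| 5,000 reads, uneven | 50% | 98% | 6.7 |
| 2,000 reads, very sparse | 40% | 85% | 4.1 |
| Noise share 0.1 | 50% | 99% | not recorded |
| Noise share 0.3 | 2% | 59% | not recorded |
| Noise share 0.5 | 1% | 9% | not recorded |

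A separate count-based run (30 runs per setting, 16 draws) gave 87-100% at 0.2 with about 6 to 11 hits, against 3-13% after one pooled BH step.

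**Step 5: the reported pattern.** Every hit at 0.05 is also a hit at 0.2. Subtracting the two columns therefore gives the share of null trials with nothing at 0.05 but something at 0.2. From the top row down: 30%, 28%, 48%, 45%, 49%, 57%, 8%. Except in the noisiest setting, the reported result is an ordinary outcome when nothing differs.

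**The case against.** The strongest reply is that separate correction by contrast and level is nowhere stated. Correction across all taxa tested could mean one pooled step, and one padj per taxon per comparison describes the output, not the family. Under pooling the excess largely disappears (Step 3). The emmeans p-values may also already have been adjusted across contrasts. This stands: per-family correction is an inference. It is the natural one, since data are prepared level by level and the only dimension named for correction is taxa.

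A reader might go further and infer that about 56 families each spent a 5% allowance, so that a false finding at 0.05 was likely. The documents do not support that. No taxon passed 0.05, so that cut-off produced no claim. After averaging, the chance at 0.05 runs from about 1% to 70% depending on noise. The count of 56 is derived from the schedule and is not printed.

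The simulations are also small and rest on assumed taxa counts, depths and variances. At 85% of 60 runs the standard error is sqrt(0.85 x 0.15 / 60) = 4.6 percentage points. That limits precision, but the contrast with pooled correction remains large in the count-based settings.

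Finally, the protocol does set a priority: the acne patients' visits over time. That is a set of comparisons, not one contrast, and the taxon analysis does not use it to limit what was tested.

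**Conclusion.** The concern holds in a limited form. The FDR family and the contrast list are undefined, and no control across contrasts or levels is described. If BH was run per contrast and level, a handful of taxa at padj < 0.2 is what a complete null can produce: 85-100% of null trials in the count-based settings, but as low as 9% if Monte-Carlo noise makes up half the test-statistic variance. This rests on about 56 families (36 to 112), BH as the FDR variant, unadjusted contrast p-values, and assumed taxa counts and noise.

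A reader might infer that the reported taxa are false. The documents do not show that. They show only that the described procedure cannot separate those taxa from chance. Relaxing the cut-off after a null result compounds the problem, because it raised the allowance per family from 5% to 20%.

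**What to change.** - List every contrast that was tested, and state the FDR variant and the emmeans adjustment setting.
- Take unadjusted emmeans p-values. Within each Monte-Carlo instance, apply BH once over all taxa x listed contrasts, either at one level or over all four, and then average.
- Keep 0.05 as the cut-off for calling a taxon significant. Report the padj < 0.2 taxa as exploratory, without wording that says they differ significantly.
- Because results are known, do not present a newly chosen contrast or level as a pre-specified primary. Any priority should follow the within-acne-arm comparisons over time that the Data Analysis section already names as primary (3 visit pairs x 2 arms = 6 contrasts).

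The cost is a change of wording and a re-run of the adjustment on existing model output, with no new data. Adjusted p-values will generally be larger, and the few reported taxa may no longer be called significant.
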